4. STUDY DESIGN

This is a multi-center, prospective cohort study with a comparison to historical control to collect 2-year safety and effectiveness data on 120 subjects, at approximately 6 sites in the United States, who have undergone Navio System-assisted TKA.

Subject data will be evaluated at the pre-operative, operative, one month, six months, one year, and two year follow up visits.

A final analysis will be conducted once all subjects have completed a two year visit.

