8.3. Conditions for Study Termination

All reasonable efforts should be made to retain the subjects for the 2 year duration of this study. If the subject has a revision of any component, the subject will be terminated from the study.

A. Screening Failure

If a subject has provided consent, completed screening and for any reason is not operated on by the study device and does not receive a total knee implant from the Journey II BCS or Cruciate-Retraining (CR) Systems, the subject will not be considered enrolled in the study.

For these subjects an Inclusion/Exclusion and Informed Consent CRF, Demographics CRF, Medical History CRF, and End of Study CRF need to be completed. However, the CRFs should not be submitted into the Sponsor's database unless the subject signed consent and was assigned a Subject ID.

B. Voluntary Withdrawal

Study participation is voluntary and subjects may withdraw at any point during the study without giving their reason for doing so. An End of Study CRF will be completed for all subjects who do not finish the study, and reason for withdrawal will be documented in the form.

C. Lost to Follow-Up

Some actively enrolled subjects may not return for follow-up exams due to a variety of reasons. Study personnel must make reasonable efforts to contact the subject and document the following contact attempts prior to declaring a subject to be lost to follow-up: the subject has been contacted according to the site's policies, but no less than 2 documented phone contacts and 1 certified letter without response. Copies of all attempts to reach the subjects per regular mail or email and/or the attempts to contact the subject via other means should be documented and that documentation should be kept with the subjects CRF at the site. A subject will be considered lost to follow-up if he/she does not appear for the scheduled study visit for 2 consecutive visits and study personnel are unable to contact the subject.

D. Study Termination by Investigator/Sponsor

The Investigator **may** withdraw subjects from the study for many reasons, including but not limited to the following:

- subject noncompliance to study schematic
- subject lost to follow-up

The Investigator **should** withdraw subjects from the study:

- in case any component of the original Journey II hardware is revised/exchanged
- if the Investigator or the Sponsor stops the study for any reason

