10.3. Missing Data

A complete disposition report, along with the explanation for lost-to-follow-up, death, revision, and withdrawn subjects is to be provided in the Clinical Study Report (CSR). The methods used to handle missing or incomplete data for the efficacy and safety measures will be detailed in the Statistical Analysis Plan (SAP).

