10.4. Analysis Populations

All subjects that are operated on by the study device are considered study participants. The following study populations and analysis sets will be defined:

- **Safety Population:** This population will include all subjects that received the study device and will be used for analysis of demographics, disposition data and safety.
- **Modified Intention to Treat Population (mITT):** Following the intention to treat principle, this population Full Analysis Set (FAS): This will include all subjects that received the study device and attended at least one post-baseline assessment. This population will be used for the primary analysis of all efficacy endpoints.
- **Per Protocol Population (PP):** This population will include all subjects that received the study device, meet the inclusion/exclusion criteria, attend all follow-up assessments within the specified window, and have no significant protocol deviations. Subjects that are required to be withdrawn from the study under the protocol (e.g. due to revision) will be included regardless of attendance of follow-up visits unless they are deemed to have significant protocol deviations or failed to meet the inclusion/exclusion criteria. This population will be used as secondary analysis of all efficacy endpoints.

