10.5. Analysis of Primary Endpoint

The primary endpoint of the study is the proportion of subjects achieving post-operative mechanical alignment, defined as $\pm 3^\circ$ from target, assessed at the 1 month study visit, and after undergoing a Navio assisted TKA.

The proportion defined above will be presented along with the associated two-sided 95% confidence interval, to be calculated using exact binomial methods.

Superiority of the proportion of subjects achieving post-operative mechanical alignment, after undergoing a Navio assisted TKA against those in the reference literature (Parratte et al.)⁷ will be achieved if the lower limit of the two-sided 95% confidence interval is greater than 73.4%.

Mechanical alignment will also be summarized using summary statistics.

10.6. Analysis of Secondary Endpoints:

Implant survival rate will be assessed for a final analysis using the number and proportion of subjects who had no implant revisions by the 2-year time point, the associated 95% confidence intervals will be calculated using exact binomial methods. Time to occurrence of revisions will also be analyzed using Kaplan-Meier survival analysis.

KSS, EQ-5D-5L, and FJS scores will be analyzed separately at the end of study using Repeated Measures ANOVA models, prognostic and baseline factors will be adjusted for.

Length of hospital stay, operative time (both skin to skin time and anesthetic time), and radiographic assessments will be assessed using summary statistics. Trends in operative time measures for individual investigators over the course of the study will be assessed.

10.7. Analysis of Safety Endpoints:

The safety endpoints for this study are the number of occurrences and the frequency of subjects reporting: adverse events (AE), serious adverse events (SAE), adverse device effects (ADE), serious adverse device effects (SADE), unanticipated serious adverse device effects (USADE) and device deficiencies (DevD).

In addition, for each event, the following will be summarised: seriousness, the relationship to the investigational device (Navio), relationship to implant, relationship to study procedure, outcome and either the duration of the resolved events or the duration of the events at study completion.

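### Repeated Measures ANOVA, as named for KSS, EQ-5D-5L and FJS, does not secure use of all observed scores; a likelihood-based mixed model should be specified

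*Combined protocol and SAP*

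**What the plan says.** Under section 10.6, each of the three scores (KSS, EQ-5D-5L and FJS) is to be modelled on its own once the study ends, "using Repeated Measures ANOVA models, prognostic and baseline factors will be adjusted for". The section names none of these factors. It gives no estimation method, covariance structure or SAS procedure, and does not say whether the pre-operative score is a response or a covariate.

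The schedule in section 7.1 collects each score pre-operatively and at one month, six months, one year and two years, so there are four post-operative scores per subject.

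Section 10.4 defines the mITT/FAS set: "This will include all subjects that received the study device and attended at least one post-baseline assessment". Its use is also stated: "This population will be used for the primary analysis of all efficacy endpoints". The per-protocol set, used for secondary analysis, requires subjects to "attend all follow-up assessments within the specified window, and have no significant protocol deviations". It makes an exception for subjects withdrawn under the protocol, for instance after revision, who stay in whatever their attendance.

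Section 10.3 leaves the handling of missing efficacy and safety data to the SAP. No such rule appears in the document supplied.

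Two provisions of section 8.3 bear on missing scores. On revision: "If the subject has a revision of any component, the subject will be terminated from the study". Loss to follow-up requires two consecutive missed visits plus failed contact, so a subject can miss one visit and remain in the study.

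**The concern.** The method named in section 10.6 covers several analyses that treat incomplete records differently. The multivariate or wide-format version deletes any subject with a missing score and is generally valid only if data are missing completely at random. The univariate long-format version can keep partial records but assumes sphericity, which is doubtful for visits spaced from one month to two years. Neither is a good default when gaps are foreseeable: revision ends follow-up, single visits can be missed, and some loss is already expected at one month.

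At stake are the precision of the patient-reported results and their freedom from selection. The study is single-arm, so no concurrent group would share a shift caused by losing partial records. Documenting patient-reported outcomes is one of the study's stated purposes (section 1.2).

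**Working it through.** **Plan's own figure.** There is none to reproduce. The plan states no power, sample size or expected missingness for these three scores. Its only loss figure is about 5% at one month (section 10.1). The rates below are therefore assumptions.

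**Step 1: the sections side by side.** Section 10.4 counts a subject with one post-baseline visit in the primary efficacy set. It also keeps revision withdrawals in the per-protocol set. A complete-case model would remove both groups from the estimates although they belong to the sets. A model using all observed scores would honour both definitions. Section 10.6 does not say which applies.

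**Step 2: size under a complete-case analysis.** Inputs: N = 120 subjects (section 10.1), four post-operative visits (section 7.1), and an assumed loss m per visit, with p = 1 − m.

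- Subjects with all four scores: 120·p⁴.
- Scores used: 4 × 120·p⁴ = 480·p⁴.
- Scores observed if missed visits are independent: 480·p. Share discarded: 1 − p³.
- Scores observed if loss is monotone dropout: 120·(p + p² + p³ + p⁴). Share discarded: 1 − 4p⁴/(p + p² + p³ + p⁴).

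| m per visit | Complete subjects | Scores used | Observed, independent | Discarded | Observed, monotone | Discarded |
|---|---|---|---|---|---|---|
| 2% | 110.7 | 442.7 | 470.4 | 5.9% | 456.5 | 3.0% |
| 5% | 97.7 | 391.0 | 456.0 | 14.3% | 422.9 | 7.6% |
| 10% | 78.7 | 314.9 | 432.0 | 27.1% | 371.4 | 15.2% |
| 15% | 62.6 | 250.6 | 408.0 | 38.6% | 325.0 | 22.9% |

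For example, at m = 5%: 0.95⁴ = 0.8145, and 120 × 0.8145 = 97.7. With independent absence, 1 − 0.95³ = 14.3% is discarded. With dropout, 1 − 3.2580/3.5244 = 7.6% is discarded.

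**Step 3: effect on an estimate.** A simulation with 400 replicates compared complete cases with maximum likelihood under an unstructured multivariate normal model. The target was the change from pre-operative to two years. Assumptions: N = 120, scores in SD units, correlation 0.5 between visits. In the missing-at-random case, dropout depended on the previous score, with a log-odds slope of 1 per SD.

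| Mechanism, base rate per visit | Bias, complete case | Bias, likelihood | SE, complete case | SE, likelihood |
|---|---|---|---|---|
| Completely at random, 5% | −0.006 | −0.006 | 0.104 | 0.092 |
| Completely at random, 10% | 0.013 | 0.008 | 0.119 | 0.099 |
| At random, 5% | −0.032 | −0.001 | 0.102 | 0.099 |
| At random, 10% | −0.055 | −0.001 | 0.117 | 0.119 |

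Under completely random absence there is no material bias, and the complete-case standard error is larger by 0.104/0.092 = 1.13 and 0.119/0.099 = 1.20. Under missing at random the standard errors are similar, but the complete-case estimate is biased by about 0.03 and 0.06 SD and the likelihood estimate is not.

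**The case against.** The strongest reply is that the plan contains no deletion rule. A reader might infer from section 10.6 that any subject with a missed visit is dropped, or that revised subjects disappear from every time point. The text does not support either. Section 10.6 sets no complete-case rule, section 10.3 leaves missing data to the SAP, and section 10.4 points towards keeping partial records. The label is also used for long-format or likelihood models that retain them. This stands, and it limits the finding to what the named method fails to guarantee.

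Three further limits also stand.

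- The shares of 14% and 27% apply only to independent missed visits. Dropout, which is the pattern that revision produces, gives about half of that.
- That incomplete records are certain, or belong to subjects doing worse, is plausible but not documented. They are foreseeable.
- A mixed model does not cure scores missing because of revision, which may be missing not at random.

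What does not stand is the suggestion that deferral to the SAP settles the matter. Section 10.6 has already named the model, and two analysts could follow it faithfully yet analyse different subjects.

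**Conclusion.** The point holds as a weakness in the named method and its specification, not as a finding that the plan discards incomplete subjects. The complete-case form would contradict section 10.4, and the univariate form adds a sphericity assumption. A likelihood-based mixed model avoids both problems and is valid under the weaker missing-at-random assumption.

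Under assumed loss of 5% or 10% per visit, a complete-case analysis would keep about 98 or 79 of 120 subjects. It would discard about 8–14% or 15–27% of collected post-operative scores, the range running from monotone dropout to independent absence. In the simulated setting the bias was modest, at most about 0.06 SD. Loss rates after one month, the correlation and the dropout model are all assumptions.

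A reader might infer that this threatens the trial's main claim. It does not: the primary endpoint is a one-month alignment proportion, analysed separately. KSS, EQ-5D-5L and FJS are secondary, with no stated hypothesis or power. This is a low-cost improvement that should be made.

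**What to change.** For each of the three scores, replace the method with a likelihood-based mixed model for repeated measures, fitted by REML in SAS:

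- Response: all observed post-operative scores in the section 10.4 mITT/FAS set, with no requirement for complete visits.
- Fixed effects: categorical visit, pre-operative score and a list of covariates named in advance. State how a missing pre-operative score is handled.
- Covariance: unstructured across visits, with a stated fallback if the model does not converge.
- Stated assumption: missing at random.

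Because scores missing after revision may not meet that assumption, add one pre-specified sensitivity analysis that assigns a defined unfavourable score at visits after revision. The SAP must fix the value; one example is the subject's own pre-operative score.

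The cost is SAP wording, settled before analysis. It needs no extra subjects, visits, data or software. If the text of section 10.6 is also edited, the amendment process in section 11.2 applies.

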11. ETHICAL CONSIDERATIONS

11.1. Ethical Approval

In accordance with the Declaration of Helsinki and local regulations of the participating countries, sites must gain written IRB/EC approval prior to enrolling research participants in the study.

11.2. Protocol Amendments

Neither the Investigator nor the Sponsor will modify this protocol without mutual agreement. After agreement to initiate the modification - in the form of a protocol amendment - the Investigator agrees not to implement this modification until instructed to do so by the Sponsor. It will be necessary to obtain IRB/EC approval prior to implementation of any change in the protocol that may affect the scientific soundness or the rights, safety, or welfare of the subjects involved. Notification shall be submitted to the IRB/EC of the study site by the Investigator.

11.3. Informed Consent

All study subjects must sign an IRB/EC approved ICF according to 2011:ISO14155 guidelines, GCP guidelines and all applicable national regulations. Potential subjects must be informed as to the purpose of the study and the potential risks and benefits known or that can be reasonably predicted or expected as described in the written consent form. The subject shall have sufficient opportunity to consider participation in the study; a subject cannot be led to believe that he/she is waiving his/her rights as a subject or the liability of the Sponsor or Investigator. Subjects are then invited to sign and date the consent form, indicating their consent for enrollment. The Investigator will retain the original copy of the signed consent form in the study files. A duplicate copy shall be provided to the subject.

11.4. Risk – Benefit Analysis

A. Study Related Risks

Possible risks that may occur as a result of study procedures are:

- Subjects will be asked to complete questionnaires; however these are not interventional procedures and are not expected to add significant time to any appointments.
- This study involves the use of x-ray evaluation. X-ray exposure is cumulative over a lifetime and total exposure should be kept to a minimum. However, if the x-ray exposure when participating in the

study is equivalent to the exposure the subject would receive if they chose not to participate in the study, there is no additional risk associated with this study.

- As a result of participating in the study there could be a risk of loss of protected subject information confidentiality. All applicable confidentiality standards and data protection and privacy laws will be followed by the Sponsor to ensure that data collected is handled in confidence. Data will be coded and handled only by appropriately qualified and authorized personnel.

Risks related to the general surgical procedures are not considered here because these could be present regardless of participation into the study.

B. Study Related Benefits

Because the surgery and all the follow-up visits are the same as if the subject would not participate in this study, there are no additional medical benefits associated with participating in this study. The information gained from this study may help improve the treatment of people that need to undergo TKA.

12. MONITORING PROCEDURES

12.1. Source Documentation

Investigators are responsible for obtaining and maintaining complete subject health information in the medical record for each subject (source documents). Examples of source documents follows: hospital records, clinic and office charts, memoranda, dispensing records, subject questionnaires, clinic evaluation transcriptions, operative notes, x-rays, radiology reports, blood collection reports and shipment records, and research subject files.

Original CRFs may be used as source documents only in the case of 2011 Knee Society Score, Quality of Life (EQ-5D) and the Forgotten Joint Score.

The Principal Investigator shall ensure that clinical records are clearly marked to indicate that the subject is enrolled in a particular clinical study and if he/she completed per protocol or discontinued early and the reason.

12.2. Direct Access

This study may be monitored by the Sponsor or a qualified person designated by the Sponsor. This qualified person could be an employee of the Sponsor or of a contract research organization (Sponsor's agent).

The investigator will provide Sponsor, Sponsor's agents, IRB/EC and regulatory agencies with direct access to all source data/documents to permit study-related monitoring, audits, IRB/EC review, and regulatory inspections.

12.3. Site Qualification Visit

A site qualification visit may be performed by the Sponsor prior to the execution of a clinical agreement to ensure that all Investigators have the appropriate training, staff, facilities and resources to adequately conduct the study.

12.4. Site Initiation Visit

A site initiation visit to provide training on the specifics of the study, site obligations and expectations of study conduct will be performed by the Sponsor. No screening or other study procedures may be performed prior to the execution of the Clinical Study Agreement and documented IRB/EC approval.

12.5. Interim Monitoring Visits

The Sponsor or its designee will conduct the appropriate site visits at the appropriate intervals. The clinical investigation will be monitored to ensure that: the rights and wellbeing of the subjects are protected; the reported data are accurate, complete, and verifiable from the source documents; and the study is conducted in compliance with currently approved protocol, with GCP regulations, and with applicable regulatory requirements. Detailed monitoring requirements will be documented within the Clinical Monitoring Plan for this study.

12.6. Closeout Visit

A study close out visit will be performed by the Sponsor or designee to retrieve and account for all remaining clinical data and to resolve outstanding queries. During study close-out, the monitor will review investigator files to ensure required documents and records are on file, confirm the disposition of any other ancillary items used for the study, and review regulatory requirements regarding records retention and IRB/EC reporting requirements.

12.7. Sponsor Audits and Regulatory Inspection

The Sponsor, Sponsor's agents, IRB/EC and regulatory agencies may audit study data. The site must accommodate audit requests, notify the Sponsor of any requests as soon as they are received, and provide direct access to study records during the audit.

12.8. Data Handling and Record Keeping Requirements

Case report forms (CRFs) will be supplied by the Sponsor. Subjects will be identified by a study number and subject identification code. Only the Investigator site will have the key to identify individual subjects. The Investigator is responsible for the timely and accurate completion of CRFs. All documents related to the study must be securely archived at the study site or in a central archive.

Data required according to this protocol are to be recorded on the case report forms (CRFs) at the time of the scheduled visits. Once a subject is enrolled, completed CRFs should be sent to the Sponsor, either by fax or by e-mail, as soon as possible, and is generally expected within 10 working days upon completion of the CRFs.

12.9. Data Recording and Record Retention

Clinical research records shall be stored in a manner that ensures privacy, confidentiality, security and accessibility of the records both during and after the conduct of the study. The Investigator/Institution will take measures to prevent accidental or premature destruction of those documents. The investigator must retain essential study documents for at least 2 years after the latest of the following: the date the study is terminated or completed or the date the documents are no longer needed to support a premarket approval application. If the Investigator needs to dispose of the documents, the Sponsor should be contacted for approval prior to disposal or destruction. For discontinued product, the essential documents will be retained until at least 2 years have elapsed since the formal discontinuation (via notification of the FDA or other regulatory agency) of clinical development of the investigational product. The investigator will retain these documents for a longer period if required by the applicable local laws.

If the responsible investigator retires, relocates, or withdraws from responsibility of keeping the study records, custody must be transferred to a person who will accept the responsibility. The Sponsor must be notified in writing of the name and address of the new custodian. Under no circumstance shall the Investigator relocate or dispose of any study documents before having obtained written approval from the Sponsor.

